11.1.7. Clinical Laboratory Tests

Serum chemistry tests include albumin, alkaline phosphatase (ALP), alanine aminotransferase (ALT), aspartate aminotransferase (AST), urea nitrogen, calcium, bicarbonate, creatinine, globulin, glucose, phosphorus, potassium, sodium, total bilirubin, total cholesterol, total protein, triglycerides, magnesium, and uric acid.

Hematology tests include hematocrit, hemoglobin, platelet count, red blood cell (RBC) count, and white blood cell (WBC) count with differentials (neutrophils, lymphocytes, monocytes, eosinophils, and basophils).

11.1.8. Pregnancy

In the event that a female subject becomes pregnant following administration of ALD403 or may have been pregnant at the time of ALD403 exposure, or the partner of a male subject becomes pregnant following ALD403 administration to the male subject, the pregnancy must be reported to Alder within five business days of the Investigator becoming aware of the pregnancy.

Pregnancy information will be reported to Alder using the Exposure In-Utero Forms in EDC. An Exposure In-Utero Notification Form should be used to report a pregnancy that occurs within 30 days after completion of the trial.

Although pregnancy *per se* is not considered an AE, the outcome of a pregnancy that results in a birth defect or congenital anomaly or hospitalization for any reason is considered to be an SAE. Every attempt should be made to follow a pregnancy to conclusion.

Follow-up information is to be collected by the Investigator and provided to Alder regarding:

- The course of the pregnancy including perinatal and neonatal outcome, premature termination of the pregnancy, or miscarriage
- Offspring information including birth weight and birth defects (if any)

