11. ASSESSMENT OF SAFETY

11.1. Adverse Events

11.1.1. Definitions

An adverse event (AE) is any untoward medical occurrence in a patient or clinical investigation participant administered a pharmaceutical product that does not necessarily have a causal relationship with the treatment. An AE can therefore be any unfavorable and unintended sign (including an abnormal laboratory finding), symptom, or disease temporally associated with the use of a medicinal (investigational) product, whether or not related to the medicinal (investigational) product. (ICH E6)

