- Important medical events that may not result in death, be life-threatening or require hospitalization may be considered serious when, based upon appropriate medical judgement, they may jeopardize the patient or subject and/or may require medical or surgical intervention to prevent one of the outcomes listed in the definition (21 CFR 312.32(a) and ICH E2A).

Of note:

- A social hospitalization (i.e., hospitalizations for pre-admissions not due to an acute medical issue) is not considered an SAE.
- Hospitalization is considered a greater than 24 hour hospital admission.

Severity

The severity of an AE will be graded as follows:

- Grade 1 Mild; asymptomatic or mild symptoms; clinical or diagnostic observations only; intervention not indicated.
- Grade 2 Moderate; minimal, local, or noninvasive intervention indicated; limiting age-appropriate instrumental Activities of Daily Living (ADL).
- Grade 3 Severe or medically significant but not immediately life-threatening; hospitalization or prolongation of hospitalization indicated; disabling; limiting self-care ADL.
- Grade 4 Life-threatening consequences; urgent intervention indicated.
- Grade 5 Death related to AE.

Relationship to ALD403

The Investigator is required to assess the causality/relationship between each AE and the ALD403 as not related or related and record the assessment on the source documents and in the eCRF AE page. Medical judgment should be used to determine the likely relationship of the AE to the ALD403 considering all relevant factors including (but not limited to) relevant history, concomitant medical condition, and concomitant medications. Determination should be based on assessment of temporal relationships, biologic plausibility, association (or lack of association) with underlying disease, and presence (or absence) of a more likely cause.

Not Related: It is plausible that the AE has an etiology other than the ALD403 (e.g., pre-existing condition, underlying disease, concomitant medical condition, or concomitant medication).

Related: The AE cannot reasonably be explained by the subject's clinical state, concomitant\medical condition or concomitant therapies, and a temporal relationship exists between the event onset and administration of the ALD403.

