3.6.2.2 Serious Adverse Events

All SAEs will be listed and summarized in a similar manner to TEAEs.

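### Read literally, Protocol 11.1.8 makes an uncomplicated delivery with a hospital stay over 24 hours a serious adverse event

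*Protocol*

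**What the plan says.** Three parts of the protocol bear on how a birth is classified.

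- Section 11.1.1 sets the entry condition for any event: "An adverse event (AE) is any untoward medical occurrence in a patient or clinical investigation participant administered a pharmaceutical product".
- Section 11.1.2 defines the hospital criterion: "Hospitalization is considered a greater than 24 hour hospital admission". Its one exemption is this: "A social hospitalization (i.e., hospitalizations for pre-admissions not due to an acute medical issue) is not considered an SAE". Delivery is not mentioned.
- Section 11.1.8 accepts that pregnancy alone is not an AE, but continues that a pregnancy outcome leading to a congenital anomaly, a birth defect or "hospitalization for any reason is considered to be an SAE".

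On the analysis side, SAP section 3.6.2.2 says: "All SAEs will be listed and summarized in a similar manner to TEAEs". Protocol section 13.4.4.2 is to the same effect. Neither document sets deliveries apart. SAP section 3.6.7 adds a listing of positive pregnancy tests.

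**The concern.** A healthy term birth followed by a maternity stay of more than 24 hours satisfies the hospitalization limb of 11.1.8 as written. Because that limb applies whatever the cause of the stay, it leaves the investigator no room to say that nothing went wrong. The same birth would not be an AE under 11.1.1, so an event could be serious without being adverse. Section 11.1.4 would then require a report within 24 hours, and the SAP would count it.

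Long-term safety is the primary objective, SAEs are among the listed safety endpoints, and the trial has 120 planned subjects and no control arm. A delivery counted as an SAE would read as a serious harm after ALD403, with no comparator rate to set against it.

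**Working it through.** **Step 1. Apply the text to one case: a healthy baby and a maternal stay over 24 hours, before the final visit.**

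- 11.1.1: nothing untoward happened, so there is no AE.
- 11.1.2: the admission exceeds 24 hours, so it is a hospitalization. The social-admission exemption is explained in terms of pre-admissions and does not name delivery.
- 11.1.8: the outcome involved a hospitalization, and the reason is irrelevant, so it is an SAE.
- SAP 3.6.2.2: it is listed and summarized.

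Sections 11.1.1 and 11.1.8 give opposite answers for the same record. If the stay is 24 hours or less, 11.1.2 does not count it and the conflict does not arise.

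**Step 2. The plan's own figure.** Protocol 13.1 assumes that over 75% of 120 subjects complete the primary phase: 120 × 0.75 = 90, which matches the stated minimum of 90. The point does not depend on this figure, but the 75% is used in Step 4.

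**Step 3. Size per record.** The denominator is the Safety Population, planned at 120. One record in a subject with no other SAE adds 1/120 = 0.83 percentage points; two add 2/120 = 1.67. If the subject already has an SAE, the any-SAE incidence does not move.

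**Step 4. How many records?** The documents give no pregnancy rate, so every input here is an assumption unless a section is named.

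- Timing. Protocol 11.1.3 collects events to the final visit; after that, SAEs are reported only if considered related. With 37 to 40 weeks from conception to birth, conception must occur by Week 56 − 40 = 16 to 56 − 37 = 19 for a Week 56 exit, or by Week 104 − 40 = 64 to 104 − 37 = 67 for a Week 104 exit. Take 38 weeks: Weeks 18 and 66.
- Exposure. Conception in Weeks 0–18 stops treatment (8.4.1), so fewer than four infusions are given and the exit is at Week 56. Conception in Weeks 48–66 falls in the secondary phase; apply 75% retention. Exposure = 18 + 0.75 × 18 = 31.5 weeks.
- Assumed: 50 to 90 women able to conceive, 1% to 5% contraceptive failure per year, and 60% to 70% of conceptions ending in live birth.

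Births = women × annual failure rate × (31.5/52) × live-birth fraction:

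- Low: 50 × 0.01 × 0.606 × 0.60 = 0.18
- High: 90 × 0.05 × 0.606 × 0.70 = 1.91

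The documents do not say whether a woman who conceives in Weeks 36–48, after four infusions, exits at Week 56 or Week 104. If all such women stayed to Week 104, exposure would be 31.5 + 0.75 × 12 = 40.5 weeks and the high end 90 × 0.05 × (40.5/52) × 0.70 = 2.45. Both high figures still include complicated births and stays of 24 hours or less, which are not false SAEs. A working range of 0 to about 2 records is reasonable.

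**The case against.** **Rarity.** Pregnant women and those planning pregnancy are excluded (8.2, criterion 16), contraception is required (8.1, criterion 5), and treatment stops on pregnancy (8.4.1). This stands, and it limits the size; the count may well be zero.

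**The social-admission exemption.** A planned delivery admission is arguably not due to an acute medical problem, so 11.1.2 might already exempt it. This stands only in part. The exemption does not name delivery, and 11.1.8 says the reason for the stay does not matter. A site cannot tell which section governs, which is itself a reason to reconcile them.

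**Visibility.** SAEs are listed and tabulated by preferred term, positive pregnancy tests are listed, and no hypothesis test is attached. A careful reader would recognise a delivery. That is fair, but the headline SAE incidence would still include it.

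**Conservative capture.** Broad reporting of pregnancy hospitalizations can be a deliberate safety choice. However, 11.1.8 already requires every pregnancy to be reported to the sponsor within five business days and followed to its outcome, so an exemption for normal delivery loses no information.

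**Stronger readings that the documents do not support.** A reader might infer that a miscarriage managed without admission is left out of the SAEs, so that the result errs in both directions. Section 11.1.8 does name miscarriage only among the follow-up items ("The course of the pregnancy including perinatal and neonatal outcome, premature termination of the pregnancy, or miscarriage"). But a miscarriage remains an untoward occurrence under 11.1.1, and 11.1.2 provides a route without admission: "Important medical events that may not result in death, be life-threatening or require hospitalization may be considered serious when, based upon appropriate medical judgement". Classification is left to judgement; it is not ruled out. A reader might also infer that births to partners of male subjects inflate the table. Partners are outside the Safety Population (SAP 2.1), and incidence is calculated on subjects in the analysis set (SAP 3.1), so this is at most a matter for clarification.

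**Conclusion.** The pregnancy rule is wrong as written, in a narrow way. Read literally, 11.1.8 classes an uncomplicated delivery with an admission over 24 hours as an SAE, in conflict with 11.1.1 and with its own statement that pregnancy alone is not an AE. The error runs only toward over-counting, and it needs a birth before the final visit.

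The size is at most 0.83 percentage points per record. The range of 0 to about 2 records (0 to 1.67 points) rests on the assumptions in Step 4. The documents give no expected SAE count, so a proportional inflation cannot be stated. Nor do they show that the SAE result will be wrong, only that the rule would make it so if such a birth occurred.

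**What to change.** Reconcile Protocol 11.1.8 with 11.1.1 and 11.1.2 by replacing the hospitalization limb with wording such as: hospitalization for an uncomplicated delivery is not in itself an SAE; a pregnancy complication or outcome that meets a seriousness criterion in section 11.1.2, including a congenital anomaly or a miscarriage judged to be an important medical event, is an SAE.

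This keeps medical judgement for miscarriage and does not make every spontaneous abortion an automatic SAE. SAP 3.6.2.2 can stay as it is, because it follows the protocol's classification.

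The cost is one sentence in a protocol amendment and a note to sites. No new data are needed, since pregnancy outcomes are already collected under 11.1.8.

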11.1.9. Suicidal Ideation and Behavior

Recent meta-analyses, spontaneous reports, and published case reports regarding suicidal ideation and behavior arising from drugs tested in clinical trials have been noted as an area of general concern. Based on this information, the United States Food and Drug Administration (FDA) has provided guidance to prospectively assess suicidal ideation and behavior in clinical trials to ensure that subjects in clinical trials who are experiencing suicidal ideation and behavior are properly recognized and adequately treated and to ensure the collection of more timely and more complete data on suicidal ideation and behavior than have been collected in the past.¹² The C-SSRS (Columbia-Suicide Severity Rating Scale) will be used for this purpose. Any subject who answers “yes” to questions 4 or 5 of the C-SSRS during the screening visit will be referred to a mental health specialist by the Investigator. During the course of the trial after dosing, any subject who answers “yes” to questions 4 or 5 in the Suicidal Ideation section or answers “yes” to any question in the Suicidal Behavior section of the C-SSRS will be discontinued from the study treatment as specified in [Section 8.4.1](#), and referred by Investigators to a mental health specialist. Affirmative answers to questions 4 or 5 for suicidal ideation or to any question for suicidal behavior will be reported in EDC as an AE.

11.2. Management of Reactions to ALD403

There are no specific antidotes to ALD403.

Each medical emergency should be treated appropriately by the Investigator using proper standard of care, according to their typical clinical practice and local guidelines for that emergency condition. Emergency equipment and medication for the treatment of these potential adverse events must be available for immediate use.

Should a medical condition arise that the Investigator believes is related to ALD403, clinical judgment should be used to provide the appropriate response including the consideration of discontinuation of ALD403. Subjects who have experienced a potential significant allergic reaction after administration of ALD403 should not receive subsequent doses until discussed with the Medical Monitor and an appropriate disposition has been agreed upon.

If a subject experiences a potential systemic allergic reaction, as assessed by the Investigator, the site will collect additional blood specimens using the immune response lab kit at the time of the event as per laboratory manual. The Medical Monitor may request a 2nd immune response lab kit be collected in approximately 4-6 weeks after the 1st collection. This immune response assessment includes serum histamine, serum tryptase, immunoglobulin E, and complement components.

Whether maintained in a “formal crash cart” or separately, the following is a requirement at the site:

- CPR certification by site staff performing study assessments
- Automated external defibrillator (AED)
- Emergency medications including antihistamines, bronchodilators, IV saline, corticosteroids, acetaminophen, and epinephrine

The AED and emergency medication should be immediately available on an Investigational product infusion day.

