3.6.2 Deaths, Serious Adverse Events and Other Significant Adverse Events

3.6.2.1 Adverse events of special interest

Adverse events of special interest include the following and additional PTs to be determined at time of database lock;

Hypersensitivity and Anaphylactic Events

A subset of adverse events with a MedDRA coded SOC of Immune system disorders and PTs of Hypersensitivity, Anaphylactic reaction and Anaphylactoid reaction.

Events Associated with CSSRS

A subset of adverse events with a MedDRA coded SOC of Psychiatric disorders and PTs of Suicidal behavior, Suicidal ideation, Suicidal attempt and Self injurious behavior.

Cardiovascular Events

A subset of adverse events with a MedDRA coded SOC of Cardiac disorders and PTs of Atrial fibrillation, Bradycardia, chest pressure, Palpitations, Sinus bradycardia, Sinus tachycardia and Tachycardia.

A subset of adverse events with a MedDRA coded SOC of Investigations and PTs of Blood pressure increase, Blood pressure systolic increase, Elevated blood pressure, Heart rate increased, Heart rate decreased, Heart rate irregular, Electrocardiogram abnormal, Electrocardiogram Q wave abnormal, Electrocardiogram QT interval abnormal, and Electrocardiogram QT prolonged.

A subset of adverse events with a MedDRA coded SOC of Nervous system disorders and PTs of Seizure and Syncope.

A subset of adverse events with a MedDRA coded SOC of Vascular disorders and PTs of Flushing, Hot flush, Hypertension, Hypotension and Ischemia.

Hepatic Events

A subset of adverse events with a MedDRA coded SOC of Investigations and PTs of Alanine aminotransferase increased, Aspartate aminotransferase increased, Bilirubin increase, Hepatic enzyme increased, Liver function test abnormal, and Transaminases increased.

Events Associated with Study Drug Infusion

A subset of adverse events within one week of dosing with a MedDRA coded SOC of Skin and subcutaneous tissue disorders and PTs of Dermatitis bullous, Pruritus, Pruritus generalized, Rash, Rash macular, Rash macular-papular, Rash papular, Rash pruritic and Urticaria.

A subset of adverse events within one week of dosing with a MedDRA coded SOC of General disorders and administration site conditions and PTs of Infusion site erythema, Infusion site extravasation, Infusion site pain, Infusion site paresthesia, Infusion site pruritus, Infusion site rash, Infusion site reaction, and Infusion site swelling.

Adverse Event of Interest Analysis

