3.6.3 Clinical Laboratory Evaluations

Summary statistics for actual values and for changes from baseline will be tabulated for clinical laboratory results by scheduled visit. Subjects with clinical laboratory values outside of the normal reference range at any post-baseline assessment will be summarized. Shifts from baseline clinical laboratory values based upon the normal range and will be tabulated.

Additional blood specimens using the immune response lab kit will be collected for subjects who experience a potential systemic allergic reaction that the Investigator believes is related to ALD403. The immune response lab results will be provided in a listing.

Plots of average clinical laboratory parameters will be presented over time.

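### The SAP's hypersensitivity summary rests on three pre-specified coded terms, with no rule that brings in the allergic reactions the Investigator identified and sampled under Protocol 11.2

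*Protocol*

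**What the plan says.** Protocol 11.2 starts the immune work-up on the Investigator's judgement: "If a subject experiences a potential systemic allergic reaction, as assessed by the Investigator, the site will collect additional blood specimens". That sentence has no coded term, time window or causality condition. On content: "This immune response assessment includes serum histamine, serum tryptase, immunoglobulin E, and complement components".

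SAP 3.6.2.1 defines the hypersensitivity category by coding: "A subset of adverse events with a MedDRA coded SOC of Immune system disorders and PTs of Hypersensitivity, Anaphylactic reaction and Anaphylactoid reaction". The section opens with a provision that can lengthen the list: "Adverse events of special interest include the following and additional PTs to be determined at time of database lock". It gives no criterion for choosing those terms.

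Other signs of an allergic reaction are placed elsewhere in the same section. Urticaria, rash and pruritus terms are infusion-associated events, with a time limit: "A subset of adverse events within one week of dosing with a MedDRA coded SOC of Skin and subcutaneous tissue disorders". Vascular signs sit in the cardiovascular category, which includes "PTs of Flushing, Hot flush, Hypertension, Hypotension and Ischemia".

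SAP 3.6.3 describes who is sampled as "subjects who experience a potential systemic allergic reaction that the Investigator believes is related to ALD403", and then says: "The immune response lab results will be provided in a listing". It plans no count of these subjects and no link to the special-interest category.

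**The concern.** Long-term safety of repeat dosing is the primary objective (Protocol 6.1), and serious allergic reaction is the risk that Protocol 5.4 names for protein therapeutics. Readers will go to the hypersensitivity summary for that risk, and a low or zero entry there will be taken as reassurance.

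The summary depends on the coded term, while the trial's own recognition of the event depends on the Investigator. If a worked-up reaction is recorded by its signs, the summary can omit it although the site judged it potentially allergic and drew histamine and tryptase.

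The protocol does make such a link for another safety concern. Under 11.1.9, affirmative answers on the more severe C-SSRS ideation questions or on any behavior question must be reported as an adverse event. Nothing comparable ties an immune kit to a reporting category.

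**Working it through.** **Plan's own figure.** No stated number attaches to this point. The only derived sample-size figure is the count with one year of data (Protocol 13.1, SAP 1.3): 0.75 × 120 = 90, which reproduces. Safety summaries are descriptive (SAP 2.5), so no power or alpha calculation applies.

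**Tracing a kit-triggering reaction through SAP 3.6.2.1.** Each row is a way in which the same kind of reaction could be recorded.

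| Recorded and coded as | Pre-specified category |
|---|---|
| Hypersensitivity, Anaphylactic reaction or Anaphylactoid reaction | Hypersensitivity |
| Urticaria, or a listed rash or pruritus term, within one week of dosing | Infusion-associated |
| The same skin term, more than one week after dosing | None |
| Flushing or Hypotension | Cardiovascular |
| An airway sign, facial swelling or angioedema | None: no respiratory class and no such term is listed |

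Only the first row enters the hypersensitivity category. All five would meet the kit trigger if the Investigator judged the event a potential systemic allergic reaction.

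**The relatedness condition.** Under Protocol 11.1.2 an event is classed as not related when another cause is plausible. A reaction with a plausible alternative cause is therefore sampled under Protocol 11.2 but falls outside the group that SAP 3.6.3 describes. In Protocol 11.2 the reference to relatedness to ALD403 is in a separate paragraph on the clinical response, not in the kit sentence.

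**Illustration of size.** The documents give neither a reaction rate nor the share that would be coded to the three terms, so both are assumed here.

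(a) Exact (Clopper-Pearson) 95% limits for x subjects out of n = 120. Lower limit: the 0.025 quantile of Beta(x, n − x + 1). Upper limit: the 0.975 quantile of Beta(x + 1, n − x). For x = 0 the upper limit is 1 − 0.025^(1/120) = 3.03%.

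| Subjects counted | Percent | 95% limits |
|---|---|---|
| 0 | 0.00 | 0 to 3.03 |
| 1 | 0.83 | 0.02 to 4.56 |
| 2 | 1.67 | 0.20 to 5.89 |
| 3 | 2.50 | 0.52 to 7.13 |

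(b) Chance that at least one case enters the summary, with true rate p and share s coded to a listed term: 1 − (1 − p·s)^120. For example, p = 1% and s = 50% gives 1 − 0.995^120 = 45.2%.

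| p | s = 100% | 75% | 50% | 25% |
|---|---|---|---|---|
| 1% | 70.1% | 59.5% | 45.2% | 25.9% |
| 2% | 91.1% | 83.7% | 70.1% | 45.2% |
| 3% | 97.4% | 93.5% | 83.7% | 59.5% |

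At low rates, the chance of a zero entry depends strongly on how events are coded.

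**The case against.** The other side has four good arguments.

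1. *The list is open.* The three terms are a minimum, since further terms may be added at lock. This stands, and it rules out the reading that hypersensitivity can only ever be counted under three terms. But the clause states no criterion and is applied late, to open-label data, after a formal interim analysis (SAP 2.6.3). It can add only terms, not the Investigator's assessment: adding a general airway term would also bring in non-allergic events.

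2. *Nothing is lost from the report.* A reader might infer that a sign-coded reaction appears only in the laboratory listing or the infusion category. The documents do not support that. SAP 3.6.1 puts it in the treatment-emergent tables by class and term, the severity table and the by-subject listing. SAP 3.6.2.2 summarizes it if serious, and some signs reach the cardiovascular category. The gap is confined to the hypersensitivity grouping.

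3. *Sites are told to record diagnoses.* Protocol 11.1.3 asks Investigators to combine signs into one diagnostic term where they can. An Investigator who suspects an allergic reaction has a candidate diagnosis to record. This lowers the risk, but the instruction is conditional and does not remove it.

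4. *No pooled rate is promised.* SAP 3.6.2.1 plans special-interest output by class and term. It does not expressly plan a category proportion with a confidence interval. This also stands: the intervals above show scale and are not planned outputs.

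On relatedness, the SAP cannot change whom sites sample, and its listing sentence, read alone, covers all kit results. What remains is a wording conflict that could narrow the listing.

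**Conclusion.** The point holds as a gap in the pre-specified grouping. Under the SAP's stated rule, a reaction that the site identified and sampled as potentially allergic can be absent from the hypersensitivity summary, or counted under a different special-interest heading. The open clause on further terms may repair this but does not guarantee it.

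The size is unknown. It depends on how many such reactions occur and how many are recorded by their signs, and the documents give neither figure. Protocol 5.4 reports no serious allergic reactions in completed trials, so the numbers may be small; that is also when one omitted case changes the reading from none to some. A reader might infer that the plan will understate hypersensitivity by a definite amount. The documents do not support that.

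The differing descriptions of the sampled subjects in Protocol 11.2 and SAP 3.6.3 are a separate, smaller inconsistency that needs reconciling.

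**What to change.** In SAP 3.6.2.1, before database lock:

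- Fix the full list of preferred terms for Hypersensitivity and Anaphylactic Events, replacing the open choice at lock for this category.
- State that every treatment-emergent event for which an immune response kit was triggered under Protocol 11.2 is reported in the hypersensitivity summary, whatever its class or term. Show it as a separate line beside the listed-term count, so that both remain visible.

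In SAP 3.6.3, reconcile the description of sampled subjects with Protocol 11.2, whose kit trigger carries no relatedness condition, so that the listing covers every subject sampled. Relatedness can be a column in that listing.

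**Cost.** SAP wording and a data link, with no new procedure for subjects. Laboratory results are held outside the eCRF (Protocol 14.2.2), so kit records must be matched to adverse events by subject and date. The match should use the first collection, because Protocol 11.2 allows a second kit about 4 to 6 weeks later that is not a new event. The one downside is that some events later judged non-allergic will be included; these can be flagged in the listing.
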